### 273 Active Vision Therapy Phase for Control Group Non-responders

274 At the completion of the 17-week visit, the patient and parent will be told their treatment group

275 assignment. Patients in the control group who were not responders will be offered the

276 opportunity to complete a course of active vision therapy that will be identical to what the active

277 group received. Patients will be scheduled for in-office therapy and given the home therapy

278 programs to complete. Parents/patients will have 10 days from the masked examination to

279 decide whether or not they wish to receive the additional therapy. If they decide within the 10  
280 days, this additional therapy will be paid for by the study. If they decide after the 10 day period,  
281 they or their insurance will be required to pay for the vision therapy.  
282

### 283 Observation for Recurrence Phase

284 Active and control group treatment responders will continue in an observation phase for 12  
285 months in order to determine the rate of recidivism once treatment is discontinued. Follow-up  
286 visits will occur at 13, 26, and 52 weeks  $\pm 2$  weeks from the discontinuation of treatment.  
287

### 288 Feasibility Phase

[figure not shown]
289 Due to concerns regarding whether sites can recruit a sufficient number of eligible patients, if  
290 sites and patients can adhere to weekly office visits, and the high cost of equipment and training  
291 for sites, the randomized clinical trial will have an initial feasibility phase. The feasibility phase  
292 will consist of seven pre-selected sites, three ophthalmology sites and four optometry sites with  
293 demonstrated ability to recruit patients in the desired age group, based on ATS3 performance and  
294 documentation of availability of study-eligible patients prior to study initiation. These seven  
295 sites will enroll forty-five patients during this initial phase. All patients will be enrolled and  
296 treated in full accordance with this protocol. The primary objective of this phase is to determine  
297 the feasibility of recruiting the full sample size and successfully completing the randomized  
298 clinical trial. To this end, the experience and data collected in this phase will be used to:  
299

- 300 1. Determine availability of eligible patients and willingness of parents/patients to be  
301 randomized to the proposed treatments.
- 302 2. Determine adherence to treatment protocol (i.e., weekly visits), especially in the control  
303 group.
- 304 3. Test procedures developed to train vision therapists to administer both active and control  
305 vision therapies according to protocol. Identify possible problems with training and  
306 implementation at the site level.
- 307 4. Test feasibility of delivering an office-based vision therapy program for amblyopia in  
308 PEDIG sites, particularly the ophthalmology sites.
- 309 5. Determine success of masking.
- 310 6. To estimate the percentage of patients in the control group who were not classified as  
311 responders who elect to undergo a course of active therapy.  
312

313 In addition, during the feasibility phase, the reasons that eligible patients decline to enroll and  
314 that patients are ineligible to be enrolled into the study will be collected. This information will  
315 be used to determine whether changes in the protocol for the full scale phase could increase the  
316 number of eligible patients or willingness of eligible patients to be enrolled, such as providing  
317 computers for at home vision therapy, or increasing payments to families for travel expenses.  
318 The decision to continue the study, i.e., add additional sites and recruit the full sample size of  
319 222 patients, will be based on experience and data collected during the feasibility phase of the  
320 study.  
321  
322

323 **1.4 Study Flow Diagram**

324  
325

326

## CHAPTER 2 PATIENT ELIGIBILITY AND BASELINE TESTING

### 327 2.1 Introduction

328

329 Patients are eligible for the study when the criteria in section 2.3 are met and the following are  
330 present:

331

332 • Investigator intends to prescribe 2 hours of patching per day or patient is being switched  
333 to 2 hours of patching per day

334 • Parent/guardian is willing to bring the patient in for a one hour office visit on a weekly  
335 basis for 17 consecutive weeks

336

337 Refractive error, if present, must be corrected with glasses before enrollment into the study.  
338 Prior correction of refractive error with contact lenses is permitted, but the patient must be  
339 switched to spectacles prior to enrollment into the study and wear spectacles for the duration of  
340 the study.

### 341 2.2 Eligibility Assessment and Informed Consent

342

343 A patient is considered for the study after undergoing a routine eye examination (by a study  
344 investigator) that identifies amblyopia meeting the eligibility criteria.

345

346 For patients who appear eligible for the study following a “standard-care” examination, the study  
347 will be discussed with the child’s parent(s) or guardian(s). Parent(s) or guardian(s) who express  
348 an interest in the study will be given a parent information sheet and a copy of the informed  
349 consent form to read. Written informed consent will be obtained from the parent or guardian and  
350 the Child Assent Form will be signed by the patient prior to performing any study-specific  
351 procedures that are not part of the patient’s routine care.

### 352 2.3 Eligibility and Exclusion Criteria

353

354 The following criteria must be met for the patient to be enrolled in the study.

355

1. Age 7 to <13 years

356 2. Amblyopia associated with anisometropia, strabismus (comitant or incomitant), or both\*

357

a. Criteria for anisometropia: At least one of the following criteria must be met:

358

➤  $\geq 0.50$  D difference between eyes in spherical equivalent

359

➤  $\geq 1.50$  D difference between eyes in astigmatism in any meridian

360

b. Criteria for strabismus: At least one of the following criteria must be met:

361

➤ Heterotropia at distance and/or near fixation on examination (with or without  
362 spectacles)

363

➤ History of strabismus surgery (or botulinum)

364

➤ Documented history of strabismus which is no longer present (which in the  
365 judgment of the investigator could have caused amblyopia)

366

c. Criteria for combined mechanism amblyopia: Both of the following criteria must be  
367 met:

368

➤ Criteria for strabismus are met (see above)

369

➤  $\geq 1.00$  D difference between eyes in spherical equivalent **OR**  $\geq 1.50$  D difference  
370 between eyes in astigmatism in any meridian

371                   ▪ *Note: the spherical equivalent requirement differs from that in the definition*  
372                    *for refractive/anisometropic amblyopia*

373                   \*Additional eligibility criteria apply for patients with strabismus or combined mechanism  
374                   amblyopia. See criterion 3 below.

375                   3. No constant strabismus at near

- 376                   • If constant strabismus of any measurable degree is present at near during the eligibility  
377                   examination, the patient is not eligible.
- 378                   • Patients who have a history of constant strabismus at near prior to the eligibility  
379                   examination, but have intermittent strabismus at near at the eligibility examination are  
380                   eligible for the study, provided they meet all other eligibility criteria.
- 381                   • Patients with constant strabismus at distance with intermittent or no strabismus at near  
382                   are eligible for the study, provided they meet all other eligibility criteria.

383                   4. Visual acuity, measured using the eETDRS protocol on the Electronic Visual Acuity Tester  
384                   (EVA) (*the protocol for conducting the visual acuity testing is described in the ATS Testing*  
385                   *Procedures Manual*), meeting the following criteria:

- 386                   • Best-corrected visual acuity in the amblyopic eye between 49 and 71 letters inclusive  
387                   (20/40 to 20/100 inclusive)
- 388                   • Best-corrected visual acuity in the sound eye 79 or more letters ( $\geq 20/25$ )
- 389                   • Inter-eye acuity difference 15 or more letters ( $\geq 3$  logMAR lines) (i.e., amblyopic eye  
390                   acuity at least 3 lines worse than sound eye acuity)

391                   5. Spectacle correction for measurement of enrollment visual acuity must meet the following  
392                   criteria and be based on a cycloplegic refraction (using cyclopentolate 1%) that is no more  
393                   than 6 months prior to enrollment:

394                   a. Requirements for spectacle correction:

- 395                   ➤ Spherical equivalent must be within 0.50 D of fully correcting the anisometropia
- 396                   ➤ Hypermetropia must not be undercorrected by more than +1.50 D spherical  
397                   equivalent, and reduction in sphere must be symmetric in the two eyes
- 398                   ➤ Cylinder power in both eyes must be within 0.50 D of fully correcting the  
399                   astigmatism
- 400                   ➤ Cylinder axis in the spectacle lenses in both eyes must be within 6 degrees of the  
401                   axis of the cycloplegic refraction when cylinder power is  $\geq 1.00$  D
- 402                   ➤ Myopia of amblyopic eye greater than 0.50 D by spherical equivalent must be  
403                   corrected, and the glasses must not undercorrect the myopia by more than 0.25 D  
404                   or overcorrect it by more than 0.50 D.

405                   b. Spectacles meeting above criteria must be worn either:

- 406                   1) For 16 weeks immediately prior to enrollment/randomization, or
- 407                   2) Until visual acuity in amblyopic eye is stable (defined as two consecutive visual  
408                   acuity measurements by the same testing method at least 4 weeks apart with no  
409                   improvement of 1 logMAR line or more)
  - 410                   ▪ An acuity measurement done any of the following ways may be considered the  
411                   first of two consecutive measurements: 1) in current glasses, 2) in trial frames  
412                   with full correction of hypermetropia with cycloplegia, or 3) by having the  
413                   patient return in new glasses for the first measurement. The second acuity  
414                   measure does not have to be made through the same prescription as the first, if  
415                   the second measure is made through a more accurate prescription. *Note:*  
416                   *because this determination is a pre-study procedure, the method of measuring*  
417                   *visual acuity is not mandated, although eETDRS testing is preferred if done as*  
418                   *part of usual care.*

- 419                   ▪ Prior contact lens wear is permitted, but patients must be willing to switch to  
420                   spectacles for the duration of the study. Stability of visual acuity in spectacles  
421                   according to above criteria must be documented prior to enrollment.  
422                   ▪ Prior bifocal wear is permitted but patient must switch to and show stability  
423                   with single vision glasses before being enrolled in the study. There can be no  
424                   constant strabismus at near without the bifocals.
- 425   6. Near stereoacuity of 800 seconds of arc or better on the Randot Preschool Stereoacuity test
- 426   7. No previous home-based, office-based or computerized vision therapy or orthoptics
- 427   8. Previous or current amblyopia treatment with spectacles, contact lenses, patching, or  
428   atropine is permitted. At the time of enrollment the patient must be:
- 429       • currently patching for 2 hours per day, *or*
- 430       • ready to be switched to 2 hours per day of patching from another patching dose or  
431       from atropine, *or*
- 432       • not currently on treatment (other than spectacles or contact lenses) and ready to initiate  
433       patching for 2 hours per day.
- 434   The decision whether the patient is a suitable candidate to be switched to 2 hours per day of  
435   patching is at investigator discretion. Atropine treatment must be discontinued at least 2  
436   weeks prior to enrollment. Patients taking atropine may be switched to patching when  
437   atropine is discontinued and enrolled 2 weeks later, if the investigator does not wish to stop  
438   amblyopia for 2 weeks. All patients, regardless of prior treatment status, must meet all  
439   other eligibility criteria at the time of enrollment.
- 440   9. No known skin reactions to patch or bandage adhesives
- 441   10. Cycloplegic refraction within 6 months prior to enrollment
- 442   11. Ocular exam within 6 months prior to enrollment revealing no ocular cause for reduced  
443   visual acuity
- 444   12. No developmental disability, mental retardation, or learning disability diagnosis that in the  
445   investigator's judgment would interfere with treatment.
- 446   13. Children with attention deficit hyperactivity disorder (ADHD) may be enrolled if the  
447   investigator feels that the patient could still properly perform the therapy activities.
- 448   14. No myopia more than -6.00 D spherical equivalent in the amblyopic eye
- 449   15. No prior intraocular or refractive surgery
- 450   16. Parent does not anticipate relocation outside area of active VT Study site within the next 5  
451   months
- 452   17. Patient and parent are willing to accept randomization and be available for 17 consecutive  
453   weeks of office visits and follow up
- 454   18. Siblings of patients already enrolled in this study, and children of ophthalmologists,  
455   optometrists, orthoptists, and vision therapists are excluded.
- 456   19. Patients must have access to a computer on a daily basis.

## 457   **2.4 Examination Procedures**

### 458   **2.4.1 Historical Information**

459   Historical information to be collected will include: date of birth, gender, race, ethnicity, prior  
460   amblyopia therapy (e.g., glasses, patching, pharmacologic, filters, vision therapy), refractive  
461   correction, and history of allergy/intolerance to bandage adhesive.

462 **2.4.2 Clinical Testing for Enrollment**

- 463 1. Visual acuity in each eye (right eye first) is measured by the ATS single-surround eETDRS  
464 testing protocol on the Electronic Visual Acuity Tester. The protocol for conducting the  
465 visual acuity testing is described in the ATS Testing Procedures Manual. Aspects of the  
466 testing protocol that are specific to this study are indicated below:
- 467 • Testing must be done without cycloplegia (with spectacles, if worn) no more than 7 days  
468 prior to randomization.
  - 469 • Because the patient needs to be wearing spectacles that provide best visual acuity to be  
470 enrolled, trial frames/phoropter with a different correction cannot be used to measure  
471 acuity at enrollment.
  - 472 • If the patient has difficulty with the acuity testing, often he or she will perform better  
473 when the testing is repeated. At the investigator's discretion, acuity can be retested on  
474 the same or a subsequent day to assess eligibility.
- 475 2. Ocular motility examination
- 476 • Measurement of predominant alignment by Simultaneous Prism and Cover Test (SPCT)  
477 in primary position at distance and near.
  - 478 • Testing must be done without cycloplegia (with spectacles if worn) no more than 7 days  
479 prior to randomization
- 480 3. Ocular examination as per investigator's clinical routine to rule out a cause for reduced visual  
481 acuity other than amblyopia
- 482 ➤ if performed within prior 6 months, does not need to be repeated at time of  
483 enrollment.
- 484 4. Binocularity testing (without cycloplegia): Titmus Fly and Randot Preschool Stereoacuity  
485 test
- 486 5. Cycloplegic refraction using cyclopentolate 1% as per investigator's usual routine
- 487 ➤ if performed within prior 6 months, do not need to repeat at time of enrollment

488 **2.5 Randomization of Eligible Patients**

489  
490 Assuming that visual acuity in the amblyopic eye on the better of the initial or repeat tests is  
491 20/40 to 20/100, inclusive, and acuity in the sound eye is 20/25 or better, the patient will be  
492 randomly assigned with 1:1 probability to either (1) the Active Treatment group or (2) the  
493 Control group.

494  
495 The Jaeb Center will construct a Master Randomization List using a permuted block design  
496 stratified by site, which will specify the order of treatment group assignments. A patient is  
497 officially randomized when the randomization process is completed and a treatment assignment  
498 is obtained.

499  
500 Once a patient is randomized, that patient is included in the study and in all analyses regardless  
501 of whether the assigned treatment is received. Thus, the investigator must not randomize a  
502 patient until he/she is convinced that the parent/guardian will accept either of the treatment  
503 regimens.

504  
505 Initial therapy visit must be scheduled within 10 days of the randomization visit.

506

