### 260 Primary Analysis

261 The primary outcome measure is the proportion of patients with visual acuity of 20/25 or better

262 in the amblyopic eye at the 17-week masked exam. These patients will be considered treatment

263 responders. The primary analysis will consist of a comparison between the 2 treatment groups of

264 the proportion of treatment responders with adjustment for baseline visual acuity.

265

266 Secondary outcomes are stereoacuity at the 17-week masked exam, mean improvement in visual

267 acuity at the 17-week masked exam, and rate of improvement of visual acuity.

268

269 Sound eye visual acuity will be reported for each treatment group at the 17-week masked exam

270 as mean change from baseline, distribution of number of lines of change from baseline, and

271 number and proportion of patients losing 2 or more lines from baseline.

272

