### 8.1 Sample Size Estimation

The sample size estimate was computed based on a Fisher's exact test comparing proportions of patients in each treatment group with 20/25 or better visual acuity at the 17-week masked exam. Patients meeting this criterion will be considered a treatment success. Based on data from ATSS3 patients meeting eligibility criteria for the ATSS-VT study, it is estimated that 30% of patients in the control vision therapy group will have 20/25 or better visual acuity at the 17-week masked exam. To detect an absolute increase of 20% in the active vision therapy group to an outcome proportion of 50% with type I error of 5% (one-sided) and power of 90%, a total of 222 patients is needed. Patients who drop out of the study prior to completion of the 17 week masked exam will be counted as treatment failures in the primary outcome analysis; hence, no adjustment to the sample size has been made for dropouts.

A one-sided alpha is used as there is interest in testing only whether the outcome proportion for active vision therapy is significantly higher than for controls. If not higher, then there is no reason to use active vision therapy in clinical practice. An absolute increase in outcome proportion of 20% was chosen as the smallest improvement for which clinicians would be willing to use vision therapy in their clinical practice, given the time commitment and extra expense demanded of patients.

Counting dropouts as treatment failures may lower the expected proportion with treatment success in both treatment groups. In this case, the power for the primary outcome comparison is increased to greater than 90%. Adjustment for baseline visual acuity in the primary analysis also would be expected to improve statistical power.

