## 993 **8.2 Primary Outcome Analysis**

994

995 The primary analysis will consist of a comparison of proportions of patients in the two treatment  
996 groups who have 20/25 or better visual acuity at the 17-week outcome exam, with adjustment for  
997 baseline visual acuity, using logistic regression. The primary analysis will follow the ‘intent-to-  
998 treat’ principle in which patients are analyzed according to randomized treatment assignment,  
999 regardless of whether the treatment was actually received or completed. Dropouts will be  
1000 counted as treatment failures in the primary analysis.

1001

1002 A secondary analysis that counts study dropouts as treatment successes will be performed. The  
1003 true treatment effect must be bracketed within the estimated treatment difference obtained in the  
1004 primary analysis and this secondary analysis. If these are within 10% of each other using the  
1005 absolute difference, the primary analysis will be considered the definitive analysis. Otherwise,  
1006 both estimates will be included in the publication of study results along with a discussion of the  
1007 implications for study conclusions and patient management.

1008

1009 A secondary analysis that estimates the treatment difference based on study completers only also  
1010 will be performed.

1011

1012 The treatment effect in subgroups based on baseline factors will be assessed in preplanned  
1013 secondary analyses of the primary outcome. The subgroups of interest will be those based on  
1014 baseline amblyopic eye visual acuity, age, baseline stereoacuity, prior treatment, practice type  
1015 (ophthalmology or optometry), and treatment compliance (excellent/good or fair/poor). In  
1016 accordance with NIH guidelines, estimates of treatment effect by gender and race/ethnicity also  
1017 will be computed.

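### Randomisation is stratified by site but the primary model adjusts only for baseline acuity, so the test is mildly conservative if sites differ; the 90% power target is not at risk

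*Protocol*

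**What the plan says.** Section 2.5 has each patient "randomly assigned with 1:1 probability to either (1) the Active Treatment group or (2) the" Control group, from a master list in permuted blocks "stratified by site, which will specify the order of treatment group assignments".

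Section 8.2 defines the primary analysis as a comparison of the proportions of patients in the two treatment "groups who have 20/25 or better visual acuity at the 17-week outcome exam, with adjustment for" "baseline visual acuity, using logistic regression". The synopsis (section 1.3, Primary Analysis) gives the same comparison: "the proportion of treatment responders with adjustment for baseline visual acuity". Site is named in neither place. Practice type (ophthalmology or optometry) appears in section 8.2, but only as a subgroup factor.

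Section 8.1 assumes for the control group that "it is estimated that 30% of patients in the control vision therapy group will have 20/25 or better visual acuity", and sets the target as: "To detect an absolute increase of 20% in the active vision therapy group to an outcome proportion of 50" per cent. With "type I error of 5% (one-sided) and power of 90%, a total of 222 patients is needed". It expects some extra power from adjusting for baseline acuity and does not mention site.

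The opening of chapter 8 describes its contents as a framework that the final analysis plan will supersede. That plan is not at hand.

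**The concern.** Blocking within site keeps the arms nearly balanced at every site, so site differences contribute almost nothing to the real sampling variation of the treatment comparison. A model without site does not know this. Its standard error still allows for chance imbalance of sites between arms, so it is too large whenever sites differ in success rate. The actual type I error then falls below the nominal 5%, and some power is given up.

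The protocol gives reasons to expect some site differences. It mixes ophthalmology and optometry practices, it asks in the feasibility phase whether office-based therapy can be delivered at the ophthalmology sites in particular, and it counts dropouts as failures, so differences in retention become differences in the primary outcome. Choosing site as the stratification factor also treats it as worth balancing.

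What is at stake is efficiency and agreement between design and analysis. The error is on the safe side: no bias or excess of false positives follows.

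**Working it through.** **1. The plan's own figure.** Inputs from section 8.1: control 0.30, active 0.50, one-sided alpha 0.05, power 0.90. The mean rate is 0.40.

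Uncorrected size per arm:
n = [1.645 × √(2 × 0.40 × 0.60) + 1.282 × √(0.30 × 0.70 + 0.50 × 0.50)]² / 0.20² = (1.1396 + 0.8692)² / 0.04 = 100.9.

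With the continuity correction:
n' = (n/4) × [1 + √(1 + 4/(n × 0.20))]² = 25.22 × (1 + 1.0947)² = 110.7, so 111 per arm and 222 in total.

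Exact enumeration of the one-sided Fisher test at 111 per arm gives power 0.9001. The stated 222 reproduces. This calculation contains no site term.

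**2. Simulation of the primary model.**

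- From the protocol: 222 patients, 1:1 allocation, permuted blocks within site, one-sided 5%, and overall success rates held at 30% versus 50% in every setting.
- Assumed, because the protocol does not give them: blocks of 4; 7 equal sites (the feasibility number) or 20; baseline acuity worth 0.5 logit per SD; normal site effects with SD 0, 0.5 or 1.0 on the logit scale.
- What the SDs mean: 95% of sites would have control success rates between about 14% and 51% at SD 0.5, and between about 5% and 70% at SD 1.0.
- Replicates: 24,000 under the null and 8,000 under the alternative per setting. The Monte Carlo standard error is about √(0.05 × 0.95/24,000) = 0.0014 for the level and √(0.94 × 0.06/8,000) = 0.0027 for power.

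Three tests were compared: the protocol's model (treatment and baseline acuity, Wald test), the same model with fixed site effects, and a site-stratified Cochran-Mantel-Haenszel (CMH) test without baseline acuity.

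| Sites | Site SD | Level: protocol | Level: fixed site | Level: CMH | Power: protocol | Power: fixed site | Power: CMH |
|---|---|---|---|---|---|---|---|
| 7 | 0 | 0.049 | 0.052 | 0.050 | 0.932 | 0.936 | 0.923 |
| 7 | 0.5 | 0.045 | 0.051 | 0.049 | 0.938 | 0.945 | 0.930 |
| 7 | 1.0 | 0.039 | 0.051 | 0.048 | 0.944 | 0.963 | 0.954 |
| 20 | 0 | 0.051 | 0.058 | 0.050 | 0.937 | 0.944 | 0.925 |
| 20 | 0.5 | 0.044 | 0.055 | 0.048 | 0.936 | 0.947 | 0.929 |
| 20 | 1.0 | 0.039 | 0.059 | 0.050 | 0.944 | 0.964 | 0.952 |

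**3. Reading the table.**

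- With no site differences the protocol's model holds its level (0.049-0.051).
- At SD 0.5 it runs at 0.044-0.045 and gives up 0.7 points (0.945 − 0.938) to 1.1 points (0.947 − 0.936) against fixed site effects. At SD 1.0 it runs at 0.039 and gives up 1.9 to 2.0 points.
- With 20 sites the fixed-effects model itself runs above nominal (0.055-0.059), so part of its apparent gain there is not real.
- The CMH test holds its level (0.048-0.050) but omits baseline acuity. At SD 0.5 and below it has less power than the protocol's model, so site should be added to the acuity adjustment and not replace it.

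**4. A second simulation**, also with rates held at 30% versus 50%, gave the protocol's model a level of about 0.046-0.048 at SD 0.5 and 0.037-0.039 at SD 1.0. A site-stratified test restored the level to about 0.05 and gained about 0.2-0.5 points of power at SD 0.5 and 1.5 points at SD 1.0.

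**The case against.** The strongest case on the other side has four parts.

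- **Deferral.** Chapter 8 is a framework, the superseding plan may already include site, and stratifying by site does not commit the trial to a site term. This stands in part. The protocol does not contradict itself, but it names its primary model and covariate twice, so this is a stated choice and not a detail left open.

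- **Harmlessness.** The test errs on the safe side and still exceeds its power target. This stands, and it limits the point to one of efficiency.

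- **Plausibility.** Eligibility, acuity testing, therapy procedures and the masked outcome examination are standardised. An SD of 1.0 implies control success from about 5% to 70% across sites, which nothing in the protocol supports. This also stands: SD 0.5 is already a wide spread, and the effect there is small.

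- **Risk in the remedy.** Fixed effects for many small sites inflate the error, and a conditional model drops sites with all successes or all failures and yields no standardised risk difference. This bears on the form of the fix, not on whether to make one.

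A reader might go further and infer that leaving out site takes power below 90%. The documents do not support that. Such a result appears if the conditional effect is held fixed while site variation grows. With an intercept of −0.85, a treatment log odds ratio of 0.95 and acuity at 0.8 logit per SD, the risk difference shrinks from 20.1 points at site SD 0 to 17.5 at SD 1.0 and 16.3 at SD 1.3. Section 8.1 plans for 20 points. The lost power in that setting comes mainly from the smaller effect, which a site-adjusted test would face as well.

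**Conclusion.** The point holds as a modest matter of efficiency. Randomisation is stratified by site and the stated primary model leaves site out. If sites differ, the one-sided test runs at about 4.4-4.8% with a site SD of 0.5 and about 3.7-3.9% with an SD of 1.0. The power forgone is about 0.2-1 point in the first case and up to about 2 points in the second. If sites do not differ, there is no conservatism.

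At the planned 30% versus 50%, the protocol's model keeps about 93-94% power in every setting examined. Neither the validity of the test nor the 90% target is threatened, and 222 patients remain enough.

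The direction follows from the design. The sizes depend on assumed values for the number of sites, the block size, the effect of baseline acuity and the between-site spread, none of which the protocol gives for the full trial.

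**What to change.** In section 8.2, and in the final analysis plan that supersedes it, state that the primary analysis accounts for site as well as baseline visual acuity, either through a random site intercept in the logistic model or through a baseline-adjusted test stratified by site. Align the synopsis in section 1.3. Avoid unpooled fixed site effects, which ran at 5.5-5.9% with 20 sites. The random-intercept form was not simulated here, so its level should be checked at the expected number and size of sites before it is chosen.

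The change is a sentence in each place, with no new data and no more patients. It should be made before outcome data by arm are seen, so that the site term cannot look data-driven. The cost is a slightly more complex model and up to about 0.4 points of power if sites turn out not to differ.
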